## 2.10 Interim analysis

No formal interim analysis is planned for this trial.

However, two safety review meetings were conducted:

- One meeting after subjects included in the first cohort (treated with MBG453 at the 400 mg Q4W) have completed 2 cycles of treatment,
- A second meeting after subjects included in the second cohort (treated with MBG453 at 800 mg Q4W) have completed 2 cycles of treatment.

The decision to start enrollment in the second cohort and to continue with the MBG453 dose of 800 mg Q4W in the expansion phase will be guided by a Bayesian analysis based on the incidence of dose limiting toxicity (DLT) data.

For each cohort (MBG453 400 mg and 800 mg Q4W) of the safety run-in part, the following information (summaries and/or listings) will be provided:

- Number (%) of subjects treated and included in the analysis sets
- Basic demographic and background data
- Disease characteristics (including ELN risk category)
- Medical history
- Concomitant medications
- Patient disposition

- Protocol deviations
- Duration of exposure to study treatment
- Dose intensity and relative dose intensity
- Number (%) of subjects with any dose changes (incl. reductions, interruptions, or permanent discontinuations) and the reasons
- DLTs, AEs, treatment related AEs, SAEs, on-treatment deaths reported during the DLT evaluation period, as well as DLTs, AEs, treatment related AEs, SAEs, on-treatment deaths reported up to the data cut-off date
- AESI overview (if AESI definition is available at time of the safety review meetings)
- Posterior distribution for the risk of DLT for new subjects at the dose level tested (see [Section 2.5](#))
- Laboratory data and vital signs abnormalities
- Blast counts from bone marrow, extramedullary disease assessment and investigator's response assessment
- MBG453 concentrations (what is available)
- ADA concentrations (what is available)

For the regular safety review meetings conducted after the safety run-in part, the same information as listed above will be provided except the investigator's response assessment.

The exact list of tables, listings and figures prepared for those safety review meetings will be defined in a separate planning document (e.g. TFL).

### **3. Sample size calculation**

#### **DLT analysis (safety run-in part):**

No formal statistical power calculations to determine sample size were performed for this part of the study. In the case that MBG453 administered at 400 mg Q4W with the fixed dose combination of azacitidine plus venetoclax is confirmed to be safe and tolerated in the first 3 to 6 subjects, an additional cohort of 9 to 12 subjects treated with MBG453 administered at 800 mg Q4W will be enrolled.

#### **CR analysis (safety run-in and expansion parts):**

The sample size calculation is based on the Complete Remission (CR) rate (primary efficacy endpoint) observed in subjects treated with MBG453 at 800 mg Q4W (from both safety run-in and expansion parts). The hypotheses to be tested and details of the testing strategy are described in [Section 2.5.2](#).

Based on available data ([Pollyea D. et al 2018](#)), the CR rate with the combination azacitidine+venetoclax is expected to be around 50%. The first criteria to declare the trial successful is to test if the CR with MBG453 in combination with azacitidine and venetoclax is superior to 50% (statistical significance). The second criteria is to obtain a minimum estimated effect size of at least 61% for the CR (clinical relevance).

The Bayesian formulation of this dual criterion design can be expressed as below:

- Bayesian statistical significance: probability for a positive treatment effect (i.e. CR rate  $\geq 50\% | \text{data}$ )  $\geq 0.975$
- Clinical relevance: posterior median of CR rate  $\geq 61\%$

With two criteria stated above the minimally required sample ( $n_{\min}$ ) size is 76 and the final sample size was set to 80. For 80 subjects, the table below shows data scenarios (number of responders) with respective inferential results and decisions. The minimum number of responders to declare this trial successful (both statistical significance and clinical relevance met) is 49 out of 80 subjects (61%). Based on simulations (Table 3-1), a total of 49 responders out of 80 results in a posterior median CR rate of 61.1% and a posterior probability for a positive effect ( $\text{CR} > 50\%$ ) of 0.978. If the number of responders is less than 49, both criteria are missed (NO-GO). A uniform informative Beta (1,1) prior with mean 50% has been used in these calculations.

**Table 3-1 Data scenarios, inferential results and decisions (n=80)**

True CR rate	Posterior median CR	Posterior probability for a positive effect (CR>50%)	Decision for trial success
44/80 (55.0%)	54.9%	0.813	Failed
45/80 (56.3%)	56.1%	0.867	Failed
46/80 (57.5%)	57.4%	0.909	Failed
47/80 (58.8%)	58.6%	0.940	Failed
48/80 (60.0%)	59.8%	0.962	Failed
49/80 (61.3%)	61.1%	0.978	Successful
50/80 (62.5%)	62.3%	0.987	Successful

Operating characteristics for various true CR rates are presented in the table below. The type-I error under the null value (CR rate = 50%) is 2.8% and power is 79.5% assuming a true CR of 65%.

**Table 3-2 Operating characteristics for various true CR rate (n=80)**

True CR rate	Probability of success (Go)	Probability of failure (No-Go)
40/80 (50.0%)*	0.028	0.972
44/80 (55.0%)	0.156	0.844
46/80 (57.5%)	0.287	0.713
48/80 (60.0%)	0.458	0.542
49/80 (61.3%)	0.549	0.451
50/80 (62.5%)	0.639	0.361
52/80 (65.0)**	0.795	0.205
54/80 (67.5%)	0.904	0.096
56/80 (70.0%)	0.964	0.036

\*For a true CR rate of 50% (null value), the probability for a trial success is 2.8% (type-I error).

\*\*For a true CR rate of 65%, the probability for a trial success is 79.5% (power).

These calculations were made using the software R (version 3.4.3) using the RBesT package.

## 4. Change to protocol specified analyses

Not applicable.

## 5. Appendix

### 5.1 General definitions

#### **Date of first administration of study treatment component (MBG453 or azacitidine or venetoclax)**

The date of first administration of a study treatment component (MBG453 or azacitidine or venetoclax) is defined as the first date when a non-zero dose of the respective study treatment component is administered and recorded on the study treatment eCRF page.

#### **Date of last administration of study treatment component (MBG453 or azacitidine or venetoclax)**

The date of last administration of a study treatment component (MBG453 or azacitidine or venetoclax) is defined as the last date when a non-zero dose of the respective study treatment component is administered and recorded on the study treatment eCRF page. So both, first and last date of study treatment component, are derived separately for each drug which is part of the study treatment.

#### **Date of first administration of study treatment (combination)**

The date of first administration of study treatment (or start date of study treatment) is defined as the first date when a non-zero dose of any component of the study treatment (MBG453, azacitidine or venetoclax) is administered.

#### **Date of last administration of study treatment (combination)**

The date of last administration of study treatment (or start date of study treatment) is defined as the last date when the last non-zero dose of any last component of the study treatment (MBG453, azacitidine or venetoclax) is administered.

#### **Date of last exposure to study treatment component (MBG453 or azacitidine or venetoclax)**

One planned cycle length is 28 days and the start date of a cycle is defined as the first administration of azacitidine within a cycle. Azacitidine is planned to be administered daily every cycle during 7 days at the beginning of each cycle (between Day 1 to Day 9). MBG453 is administered every 4 weeks (Q4W), on Day 8 of each cycle, unless there was a toxicity leading to a dosing interval increase. Venetoclax is planned to be administered on each day of the 28-day cycle.

The date of last exposure to MBG453 is therefore calculated as:

- Minimum (last date of administration of MBG453 + 27 days, date of death, last contact date in case subject is lost to follow-up, analysis cut-off date), as MBG453 injections are given Q4W.

The date of last exposure to azacitidine is calculated as:

- Minimum (last date of administration of azacitidine + 20 days, date of death, last contact date in case subject is lost to follow-up, analysis cut-off date) as the 7 doses of azacitidine are given in the beginning of each cycle.

The date of last exposure to venetoclax is calculated as:

- Minimum (the date of last administration of a non-zero dose of venetoclax, date of death, last contact date in case subject is lost to follow-up, analysis cut-off date), as venetoclax is given in a daily administration (in case of regimen change to “three weeks on, one week off”, the cycle would end after 7 days; in case of regimen change to “two weeks on, two week off”, the cycle would end after 14 days; in case of regimen change to “one week on, three week off”, the cycle would end after 21 days).

### **End date of the last cycle initiated**

The end date of the last cycle initiated is the maximum date between:

- The planned end date (Day 28) of the last cycle initiated when the last non-zero dose of any last component of the study treatment (MBG453 or azacitidine or venetoclax) is administered,
- The actual date of the last administration of a non-zero dose of any last component of the study treatment.

The end date of the last cycle initiated (Day 28 or beyond) will be applicable even if this date goes beyond the data cut-off date (i.e., it should not be truncated to the date of data cut-off).

### **Date of last exposure and duration of exposure to study treatment (combination)**

For the calculation of the duration of exposure to study treatment (combination), the date of last exposure to study treatment (combination) will be derived as the minimum date between:

- The latest of last date of exposure to MBG453, azacitidine and venetoclax = maximum (date of last exposure to MBG453, date of last exposure to azacitidine, date of last exposure to venetoclax),
- Date of death,
- Last contact date in case subject is lost to follow-up,
- Analysis cut-off date

The duration of exposure to study treatment (combination) will be calculated as follow: date of last exposure to study treatment (combination) - date of first administration of study treatment (combination) + 1.

## **Duration from first to last cycle initiated to calculate dose intensity and the relative dose intensity**

For the calculation of the dose intensity and relative dose intensity, the duration in days from first to last cycle initiated will be calculated as follow: end date of the last cycle initiated - date of first administration of study treatment (combination) + 1.

Thus, this derivation will be irrespective of date of death or last contact date (i.e., it should not be truncated to the date of death or date of last contact).

## **Cumulative dose, dose intensity and relative dose intensity of venetoclax**

For venetoclax, as per protocol, the full dose will be adjusted due to the concomitant administration of CYP3A inhibitors or P-gp inhibitors. By this adjustment, the intended exposure to venetoclax is assumed to remain unchanged from clinical perspective (equivalent to full daily dose 400 mg). To this end,

- Cumulative dose will be calculated by two methods. The first one is actual cumulative dose which uses the “dose administered” in Study Treatment - Venetoclax eCRF (unadjusted method), and the second one is cumulative dose which uses the adjusted “dose administered” (400 mg/day), if administered with the concomitant CYP3A inhibitors or P-gp inhibitors (adjusted method). The first is to reflect the actual amount of venetoclax a patient receives, and the second is to reflect the actual exposure to venetoclax.
- Similarly, dose intensity will also be calculated by two methods: unadjusted and adjusted methods.
- Of note, planned dose intensity of venetoclax will only be calculated by the adjusted method and will be averaged in case the full dose changed during the ramp-up period.

For example, if a subject received a full dose of venetoclax at 400 mg during the first 2 cycles (including the ramp-up period), the dose interrupted in the next 14 days and then resumed to receive full dose of venetoclax at 200 mg with the concomitant CYP3A4 inhibitors or P-gp inhibitors during the subsequent 42 days (until the end of Cycle 4). So for this subject, his venetoclax dose/exposure can be summarized as follows:

	Unadjusted method	Adjusted method
Cumulative dose	$(100+200+300)+ 400 \times 25 \text{ days} + 400 \times 28 \text{ days} + 0 \times 14 \text{ days} + 200 \times 42 \text{ days} = 30200 \text{ mg}$	$(100+200+300)+ 400 \times 25 \text{ days} + 400 \times 28 \text{ days} + 0 \times 14 \text{ days} + 400 \times 42 \text{ days} = 38600 \text{ mg}$
Dose intensity	$30200/(28 \text{ days} \times 4) \times 28 \text{ days} = 7550 \text{ mg per 28 days}$	$38600/(28 \text{ days} \times 4) \times 28 \text{ days} = 9650 \text{ mg per 28 days}$
Planned dose intensity	-	$[(100+200+300) + 400 \times 25 \text{ days} + 400 \times 28 \text{ days} + 400 \times 14 \text{ days} + 400 \times 42 \text{ days}] / (28 \text{ days} \times 4) \times 28 \text{ days} = 11050 \text{ mg per 28 days}$
Relative dose intensity	-	$9650/11050 = 87.33\%$

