The main purpose of this amendment is to allow enrollment of patients receiving moderate or strong CYP3A4 inhibitors or Pg-p inhibitors, in order to allow use of prophylactic antifungal medications (e.g. posaconazole, fluconazole or other azoles) commonly used in this patient population. This amendment expands the pool of eligible subjects, allowing enrollment of subjects more representative of the overall population with AML not suitable for intensive chemotherapy. Venetoclax is metabolized via the CYP3A4 system. Inhibitors of CYP3A4 administered concurrently with venetoclax result in higher, potentially toxic plasma levels of venetoclax. This has been studied extensively and is reflected in the prescribing information for venetoclax. It is allowed to co-administer venetoclax with strong CYP3A inhibitors, but venetoclax doses need to be reduced. As many antifungal drugs commonly used for prophylaxis or treatment of fungal infections in AML are strong CYP3A inhibitors, this amendment removes the strict ban of co-administration in lieu of dose-reduction rules for venetoclax.

In addition, the following updates have been implemented:

- Extend the restrictions on the use of live vaccines until the end of the follow-up period after the last dose of MBG453.
- Guidance has been added on the criteria for MBG453 dose management for dermatological adverse drug reactions (ADRs) and non-immune related toxicities to align with the MBG453 Investigator's Brochure.
- Guidance has been added that subjects should be monitored carefully for any skin toxicity or mucositis, and that study treatment should be discontinued for any suspected case of Stevens-Johnson syndrome (SJS), or Lyell syndrome/toxic epidermal necrolysis (TEN) to align with the MBG453 Investigator's Brochure.

Changes to the protocol

Changes to specific sections of the protocol are shown in the track changes version of the protocol using strike through red font for deletions and red underline for insertions.

Section 5.2 - Exclusion criteria

- Exclusion criterion # 10 removed to allow enrollment of subjects receiving CYP3A4 inhibitors or Pg-p inhibitors

Section 6.1 - Study treatment

- Updated to refer to the latest Pharmacy Manual for detailed administration instructions to ensure consistency between documents and compliance with compounding standards and internal guidance.

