6.2.1.1 Permitted concomitant therapy requiring caution and/or action

Medications to be used with caution during study treatment in this study are listed below. Please also refer to Appendix 2 (see [Section 16.2](#)) for detailed guidance.

Strong or moderate CYP3A4 inhibitors and P-gp inhibitors: If, such therapy is necessary, it can be introduced, under the provision that the dose of venetoclax is reduced. Recommendation for venetoclax dose, when given in combination with strong CYP3A inhibitors (e.g., posaconazole, ketoconazole, conivaptan, clarithromycin, indinavir, itraconazole, lopinavir, ritonavir, telaprevir, and voriconazole), moderate CYP3A inhibitors (e.g., erythromycin, ciprofloxacin, diltiazem, dronedarone, fluconazole, and verapamil) or P-gp inhibitors (e.g., amiodarone, azithromycin, captopril, carvedilol, felodipine, quercetin, quinidine, ranolazine, and ticagrelor) are provided in [Table 6-3](#) below.

Table 6-3 Management of potential interactions of CYP3A and P-gp inhibitors with venetoclax

Co-administered Drug	Ramp-Up Phase	Steady Daily Dose (After Ramp-Up Phase)
Posaconazole	Day 1 - 10 mg Day 2 - 20 mg Day 3 - 50 mg Day 4 - 70 mg	Reduce venetoclax dose to 70 mg
Other strong CYP3A inhibitor	Day 1 - 10 mg Day 2 - 20 mg Day 3 - 50 mg Day 4 - 100 mg	Reduce venetoclax dose to 100 mg
Moderate CYP3A inhibitor or P-gp inhibitor	Day 1 - 50 mg Day 2 - 100 mg Day 3 - 200 mg	Reduce venetoclax dose to 200 mg (at least 50% reduction)

The venetoclax dosage that was used prior to concomitant use with a strong or moderate CYP3A inhibitor or a P-gp inhibitor should be resumed 2 to 3 days after discontinuation of the inhibitor. Subjects should be instructed to avoid grapefruit products, Seville oranges, and starfruit during treatment with venetoclax as they contain inhibitors of CYP3A4.

Strong or Moderate CYP3A4 inducers: Concomitant use of venetoclax with strong CYP3A inducers (e.g., carbamazepine, phenytoin, rifampin, St.John's wort) or moderate CYP3A inducers (e.g., bosentan, efavirenz, etravirine, modafinil, nafcillin) should be avoided. Alternative treatments with less CYP3A induction should be considered.

P-gp or BCRP substrates: Co-administration of narrow therapeutic index P-gp, or BCRP substrates (e.g., digoxin, sirolimus) with venetoclax should be avoided.

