	Subsequent occurrences in next treatment cycles after achieving remission (CR, CRi, MLFS) and lasting at least 7 days	Delay subsequent treatment and monitor blood counts. Administer G-CSF if clinically indicated for neutropenia. Once the toxicity has resolved to Grade 1 or 2, resume venetoclax therapy at the same dose with a duration reduced by 7 days for each subsequent treatment cycle
Blood chemistry changes suggestive of TLS	-	Withhold treatment. If the event is resolved within 48 hours of last dose, treatment with venetoclax can be resumed at the same dose.

Event	Occurrence	Action
Events of clinical TLS or blood chemistry changes requiring more than 48 hours to resolve	-	Withhold treatment. Treatment should be resumed at a reduced dose (per the investigator discretion). When resuming treatment after interruption due to TLS, the instructions for prevention of TLS should be followed.
Grade 3 or 4 non-hematologic toxicities	First occurrence	Withhold treatment. Once the toxicity has resolved to Grade 1 or baseline level, venetoclax therapy may be resumed at the same dose.
	Subsequent occurrences	Withhold treatment. Treatment should be resumed at a reduced dose (per the investigator discretion).

Permanent discontinuation of study treatment

If the study treatment (i.e. MBG453 + azacitidine + venetoclax) is interrupted for toxicities and the start of the subsequent study treatment cycle is delayed for more than 42 consecutive days (measured from the intended start date of the new cycle (Day 29 of the previous cycle) in absence of clinical benefit for the patient per investigator assessment, the subject should be discontinued from study treatment.

At any time during the study, patients unable to tolerate one or two of the study treatment drugs may continue study treatment with only the tolerated drug(s) provided the subject benefits per investigator's judgement.

These dose changes must be recorded on the appropriate CRF.

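### Venetoclax relative dose intensity counts any non-zero dose taken with a CYP3A or P-gp inhibitor as 400 mg, so it cannot show reduced or unreduced dosing on those days

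*SAP*

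**What the plan says.** SAP Section 5.1 (Cumulative dose, dose intensity and relative dose intensity of venetoclax) starts from the premise that, once the dose has been lowered for a CYP3A or P-gp inhibitor, "the intended exposure to venetoclax is assumed to remain unchanged from clinical perspective (equivalent to full daily dose 400 mg". It then defines two cumulative doses. The unadjusted one sums the doses recorded in the eCRF. The adjusted one substitutes a fixed daily value: "400 mg/day), if administered with the concomitant CYP3A inhibitors or P-gp inhibitors (adjusted method". Of the two, "the second is to reflect the actual exposure to venetoclax".

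Cumulative dose and dose intensity are given both ways. The denominator is not: "planned dose intensity of venetoclax will only be calculated by the adjusted method". In the worked example the unadjusted cells for planned dose intensity and RDI are empty, and the only RDI shown is "9650/11050 = 87.33"%.

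The protocol sets the steady daily dose by inhibitor class (Section 6.2.1.1, Table 6-3). For posaconazole the entry is "Reduce venetoclax dose to 70 mg"; the entries are 100 mg for other strong CYP3A inhibitors and 200 mg for moderate CYP3A or P-gp inhibitors. Separately, Table 6-6 in Section 6.5.3 lowers the dose level for toxicity after clinical or prolonged tumor lysis syndrome (TLS) and after repeat Grade 3 or 4 non-hematologic toxicity: "Treatment should be resumed at a reduced dose (per the investigator discretion".

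**The concern.** The premise covers one case: a patient taking the dose that the protocol plans for that inhibitor. The derivation rule is wider. Its only trigger is co-administration, so a programmer following it would code 400 for every non-zero inhibitor day. A dose lowered further for toxicity counts as full, and so does a dose that was never lowered for the inhibitor. Neither result reflects actual exposure, which is the stated aim.

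RDI is meant to show departures from the planned dose. SAP Section 2.4.1 illustrates this with MBG453: 600 mg on average against 800 mg planned gives 0.75. Substitution removes that property for venetoclax on inhibitor days. Co-administration is unlikely to be rare: the Amendment 2 rationale in the protocol says that "many antifungal drugs commonly used for prophylaxis or treatment of fungal infections in AML are strong CYP3A inhibitors".

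**Working it through.** **Inputs.** The worked example in SAP Section 5.1 covers four 28-day cycles: ramp-up 100 + 200 + 300 mg, then 25 days and 28 days at 400 mg, 14 days interrupted, and 42 days at 200 mg with an inhibitor. Planned doses under inhibitors come from Protocol Table 6-3.

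**Step 1: reproduce the SAP figure.**
- Before the interruption: 600 + 400 × 25 + 400 × 28 = 21,800 mg.
- Adjusted: 21,800 + 0 × 14 + 400 × 42 = 38,600 mg, or 9,650 mg per 28 days.
- Planned: 21,800 + 400 × 14 + 400 × 42 = 44,200 mg, or 11,050 mg per 28 days.
- RDI = 9,650 / 11,050 = 87.33%, as stated.

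**Step 2: vary the dose taken on the 42 inhibitor days.** Let d be the daily dose taken under a moderate inhibitor (planned 200 mg). The SAP rule always adds 400 × 42. Scaling adds d × (400/200) × 42.

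| d (mg/day) | RDI, SAP rule | RDI, scaled |
|---|---|---|
| 50 | 87.33% | (21,800 + 4,200)/44,200 = 58.82% |
| 100 | 87.33% | (21,800 + 8,400)/44,200 = 68.33% |
| 200 | 87.33% | (21,800 + 16,800)/44,200 = 87.33% |
| 300 | 87.33% | (21,800 + 25,200)/44,200 = 106.33% |
| 400 | 87.33% | (21,800 + 33,600)/44,200 = 125.34% |

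The SAP rule does not respond to d. The two methods agree at the planned dose, the only case that the SAP illustrates.

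**Step 3: remove the interruption.** With 56 inhibitor days in Cycles 3 and 4, the SAP rule gives (21,800 + 400 × 56)/44,200 = 100.0% for any non-zero dose. Scaled:
- Half the planned dose, any class: (21,800 + 200 × 56)/44,200 = 74.66%.
- An unreduced 400 mg: 150.68% (moderate or P-gp), 252.04% (other strong) and 338.91% (posaconazole).

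**Step 4: ramp-up days.** If a posaconazole patient follows Table 6-3 exactly from Day 1, the literal rule counts Cycle 1 as 400 × 28 = 11,200 mg. Against the example's planned Cycle 1 (600 + 400 × 25 = 10,600 mg) that is 105.7%. Against the 11,200 mg per 28 days in SAP Section 2.4.1, which leaves out the ramp-up, it is 100%. The answer depends on a denominator that the SAP describes in two ways.

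**Step 5: does unadjusted dose intensity fill the gap?** In the Step 3 setting, half the planned dose under a moderate inhibitor (100 mg) gives (21,800 + 100 × 56)/4 = 6,850 mg per 28 days. The full planned dose under another strong inhibitor (also 100 mg) gives the same 6,850. The unadjusted figure cannot separate a further reduction from planned dosing.

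**Side check.** The example's ramp-up (100, 200, 300 mg) differs from Protocol Table 6-2 (100, 200, then 400 mg), and the two should be reconciled. With the Table 6-2 values the example RDI is 9,675/11,075 = 87.36%, so nothing here turns on it.

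**The case against.** The strongest reply is that the rule should be read with its paragraph. The SAP speaks of the full dose being adjusted for inhibitors, and its example converts a full dose of 200 mg to 400. Protocol Section 6.5.1.2 likewise credits a reduced dose as the planned dose, for DLT evaluability, only when it follows Table 6-3. The authors may well have meant that only the Table 6-3 dose maps to 400. That is plausible, but the derivation sentence contains no such condition, and it is the sentence that will be programmed.

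A second reply concerns reach, and most of it stands. A reader might infer that patients on inhibitors will show RDI near 100% whatever happens, or that the report will hide poor tolerability and dosing errors. The documents do not support that:
- Days at 0 mg stay at 0, and the duration runs over elapsed time from the first to the last cycle, so interruptions and delays lower RDI. The SAP's own inhibitor example gives 87.33%.
- For post-remission cytopenia, Table 6-6 delays treatment and later shortens it at the same dose. RDI still captures this.
- SAP Section 2.4.1 counts subjects with reductions, interruptions and discontinuations by component, with reasons that include dosing errors. Section 2.7.1 summarises AEs leading to dose adjustment or interruption, and Section 2.3.1 tabulates protocol deviations. Protocol Section 12.3 lists all dosing data.

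These outputs show that dose changes occurred. They do not restore an RDI that measures their depth.

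Third, scaling has weaknesses of its own. It assumes exposure proportional to dose within a class, for which the documents give no figure. The Table 6-3 entry for moderate and P-gp inhibitors gives 200 mg but also describes the reduction as at least half, so a lower dose might count as compliant. Both points stand and shape the fix.

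**Conclusion.** The point holds, within limits. As written, the adjusted method scores every non-zero inhibitor day as 100%, and venetoclax RDI exists only in that form. RDI therefore cannot show two things on inhibitor days: lower dose levels after clinical or prolonged TLS or repeat Grade 3 or 4 non-hematologic toxicity, and doses left unreduced.

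In the SAP example the reported 87.33% could stand for anything from 58.8% to 125.3% as the dose taken runs from 50 to 400 mg/day. Those alternatives assume a moderate inhibitor, a planned 200 mg and exposure proportional to dose. The larger figures in Step 3 are constructed extremes that show how insensitive the rule is; they do not predict what the data will show. The documents give no frequency for affected days, so the effect on the trial-level summary is unknown. RDI is a descriptive exposure summary, and the CR analysis is not affected. The change is worth making because the rule can give a wrong number and is cheap to correct.

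**What to change.** Amend the adjusted-method sentence in SAP Section 5.1 as follows:
- On inhibitor days, count the dose as 400 mg only when the dose administered is the protocol-planned dose for that inhibitor class and day.
- For any other non-zero dose, use dose administered × 400 / planned dose for that class, and state the assumption that exposure is proportional to dose within a class.
- Treat inhibitor ramp-up days the same way in numerator and denominator, and align this with the planned intensity in Section 2.4.1.
- Pre-specify how the Table 6-3 entry with the at-least-half reduction is scored, and which class applies when several inhibitors are taken or one drug is listed in two classes (clarithromycin and itraconazole appear in Protocol Table 16-9 under both strong CYP3A and P-gp inhibitors).

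The SAP example is unchanged, since 200 × 400/200 = 400. No dosing rule changes.

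The cost is mainly programming and medical review. Concomitant medications are coded by WHO Drug and ATC, which the documents do not link to inhibitor class, and the protocol says that its inhibitor lists are not comprehensive. Someone must therefore map class to dosing days. Reported RDI may be lower.
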